4.9. Pharmacokinetic (PK) Analysis

The PK analysis plan and report will be prepared separately.

4.10. Pharmacodynamic Biomarker Analysis

The pharmacodynamic analysis plan and report will be done separately.

5. INTERIM ANALYSES AND DMC MEETING

There is no interim analysis planned and no DMC meeting scheduled. The primary analyses may be performed when all randomized subjects finish DB period.

6. CHANGE FROM ANALYSIS PLANNED IN PROTOCOL

There are no changes from the statistical analyses in protocol.

7. APPENDIX

7.1. Multiple Imputation Sample SAS Code

1. Data after use of rescue/prohibited medications will be set to missing and imputed with worst post baseline scores.
2. Impute intermediate missing data. 40 datasets with a monotone missing pattern will be obtained, induced by Markov Chain Monte Carlo (MCMC) method on subjects who have not taken the prohibited medications and/or rescue medications prior to Week 16. Variables in MCMC modeling includes actual stratification factors: sex, years since first PN diagnosis, treatment, baseline score, and percent change scores of weeks 1-16.

```
proc mi data=dataset seed=201 n impute=40 out=dat_mc;  
  mcmc impute=monotone;  
  var sex years since_first_diagnosis baseline treatment_group  
  percent_change_weeks 1-16;  
  run;
```

3. For each the imputed dataset with monotone missing pattern in Step 2, the remaining missing data will be imputed using the regression method for the monotone pattern with adjustment for covariates including sex, years since first PN diagnosis, treatment, baseline score, and scores of weeks 1-16 as covariates..

```
proc mi data=dat_mc n impute=1 seed=201 out=dat_mi;  
  by _imputation_;  
  class sex years since_first_diagnosis treatment_group;  
  monotone method=reg;  
  var sex years since_first_diagnosis baseline treatment_group  
  percent_change_week 1-16;  
  run;
```

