1.2. Study Design

This is a randomized, double-blind, placebo-controlled study to investigate the efficacy, safety, tolerability, PK, and immunogenicity of KPL-716 administered SC in subjects with moderate to severe PN experiencing severe pruritus.

[figure not shown]
The Phase 2b study ([Figure 1](#)) consists of a 4-week screening period and a 16-week double-blind (DB) period, followed by a 36-week open-label-extension (OLE) period. Approximately 180

subjects with moderate to severe PN experiencing severe pruritus will be randomized (at 1:1:1:1 ratio) into one of the following 4 arms:

- Arm A: KPL-716, 540 mg, SC, every 4 weeks (Q4W)
- Arm B: KPL-716, 360 mg, SC, Q4W
- Arm C: KPL-716, 120 mg, SC, Q4W
- Arm D: Placebo, SC, Q4W

A total of 4 doses of study drug will be administered during the DB Period to measure the efficacy, safety, and PK of KPL-716.

Figure 1 Phase 2b Study Design Diagram

After the DB period, all subjects will have the option to receive KPL-716 360 mg SC, Q2W during the OLE period to evaluate the long-term safety and PK of KPL-716. For subjects who complete the DB period but choose not to participate in OLE, or who terminate earlier, an End of Study (EOS) visit will be required 4 weeks following the date of last study drug dose.

Subjects will follow the schedule below:

- Screening period (minimum 7 days and maximum 28 days)
- DB period (Day 1 [Baseline] to Week 16)
- OLE period (End of Week 16 to Week 52)

The allowable visit window from Week 2 to Week 16 is \pm 2 days and thereafter to Week 52 is \pm 3 days.

Randomization and Dosing:

Subjects will be randomized 1:1:1:1 into one of the following 4 arms: KPL-716 540 mg SC, Q4W; KPL-716 360 mg SC, Q4W; KPL-716 120 mg SC, Q4W; or placebo SC, Q4W. At the end of DB period, all subjects will have the option to enter the OLE period to receive KPL-716

360 mg SC Q2W. Stratification will be performed based on sex and years since first nodule observed (i.e., ≥ 10 years vs. < 10 years).

Efficacy Assessments:

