1.4. Estimands

The primary estimands defined for main endpoints are summarized below in [Table 1](#). More details are provided in [Section 4.6](#).

Table 1: Summary of primary estimands for main endpoints

Endpoint Category	Estimands			Analysis set-level summary
	Endpoint(s) ^a	Analysis set	Intercurrent event(s) strategy and missing data handling	
Primary objective: To evaluate the efficacy of subcutaneous (SC) KPL-716 vs. placebo in reducing pruritus in prurigo nodularis (PN) subjects experiencing severe pruritus				
Primary endpoint	Percent change from baseline in weekly average Worst Itch– Numeric Rating Scale (WI-NRS) at Week 16	mITT	
The intercurrent events will be handled as follows:
 
 Discontinuation of study treatment before Week 16: Off-study treatment data up to Week 16 will be included in the analysis (treatment policy strategy). Taking rescue/prohibited medications that impact efficacy analyses prior to Week 16: data will be set to missing values after the medication usage, and the participant's worst postbaseline observation before the time of the medication usage will be carried forward (WOCF) to impute missing endpoint value (hypothetical strategy) 
In addition, the missing data imputation rules are as follows:
 
 Missing data at Week 16 will be imputed with Multiple Imputation (MI) method. 	Analysis of Covariance (ANCOVA) model will be used with treatment and randomization factors of sex and years since the first nodule observed (i.e., ≥ 10 vs. <10 years) as fixed effect factors, baseline as covariate.

Endpoint Category	Estimands			Analysis set-level summary
	Endpoint(s) ^a	Analysis set	Intercurrent event(s) strategy and missing data handling	

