4.6. Efficacy Analyses

All efficacy analyses will be performed in the mITT analysis set. Actual stratification factors based on EDC data will be used for efficacy analyses. The statistical analyses of the primary and key secondary endpoints will be repeated in PP analysis set. Analysis based on the mITT analysis set will be the primary analysis and the analyses based on other analysis sets will be considered as the supportive analyses.

Descriptive statistics will be provided for OLE data analyses in observed cases by all randomized subjects who enter OLE period as well as the DB treatment group, unless otherwise specified.

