4.6.2. Analyses of Primary Efficacy Endpoint

The primary analysis for the efficacy endpoints will be based on the mITT analysis set.

The following null hypothesis (H0) and alternative hypothesis (H1) will be tested for each KPL-716 dose against placebo:

- H0: No treatment difference between KPL-716 and placebo.
- H1: There is a treatment difference between KPL-716 and placebo.

The primary estimand for the primary endpoint is defined in [Table 1](#), using the treatment policy/hypothetical strategies. Off-study treatment data up to Week 16 will be included in the analysis. Data will be set to missing values after prohibited/rescue medication that impact efficacy analyses prior to Week 16, and the subject's worst post baseline observation before the time of the medication usage will be carried forward (WOCF) to impute missing endpoint value (for subjects whose postbaseline values are all missing, the baseline will be used to impute).

Missing data at Week 16 will be imputed with Multiple Imputation (MI) method. This MI method will use subjects excluding those who used prohibited/rescue medications that impact efficacy analyses prior to Week 16 as input. See [Appendix 7.1](#) for the sample SAS code for the imputation.

Each of the imputed complete data will be analyzed by fitting an ANCOVA model with treatment and randomization stratification factors of sex and years since the first nodule observed (i.e., ≥ 10 vs. < 10 years) as fixed effect factors, baseline as covariate. The imputation number will be about 40. Statistical inference obtained from all imputed data will be combined using Rubin's rule. Descriptive statistics including number of subjects, mean, standard error, and least squares

(LS) mean percent changes (and standard error) will be provided. In addition, difference of each KPL 716 dose group against placebo in LS means and the corresponding 95% confidence intervals (CI) will be provided along with the p-values

Sensitivity analyses

The sensitivity analyses will be conducted for the same estimand for the primary endpoint. There are two sensitivity analyses planned for the primary efficacy endpoint to handle missing data at Week 16 after the WOCF method is applied for the subjects who use prohibited/rescue medications that impact efficacy.

- Sensitivity 1 (WOCF/LOCF): Missing data at Week 16 will be imputed with last observation carried forward (LOCF) method.

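### The imputation model in SAP Appendix 7.1 names years since first PN diagnosis as a stratification factor, but the trial stratifies and analyses by years since first nodule

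*SAP*

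**What the plan says.** SAP 1.2 defines the randomization strata: "Stratification will be performed based on sex and years since first nodule observed", with the cut at 10 years. Protocol 5.3 says the same. The primary estimand in SAP 1.4, Table 1, specifies an ANCOVA with "treatment and randomization factors of sex and years since the first nodule observed" as fixed effects, and SAP 4.6.2 repeats this as "randomization stratification factors of sex and years since the first nodule observed". The CMH tests in SAP 4.6.3 and the subgroups in Table 8 also use time since first nodule. SAP 4.6 sets a general rule: "Actual stratification factors based on EDC data will be used for efficacy analyses".

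SAP 4.6.2 gives the subjects used as input to the imputation, the number of imputations (about 40) and the combination by Rubin's rule. It does not list the imputation covariates; it refers to Appendix 7.1 "for the sample SAS code for the imputation".

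The step 2 text of Appendix 7.1 reads: "Variables in MCMC modeling includes actual stratification factors: sex, years since first PN diagnosis, treatment, baseline score". The step 3 text describes a regression "with adjustment for covariates including sex, years since first PN diagnosis, treatment, baseline score". The step 3 code declares "class sex years since_first_diagnosis treatment_group" as categorical, and the variable lists of both steps name time since diagnosis. Years since first nodule does not appear in the appendix.

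**The concern.** The two durations are different variables. The protocol (synopsis and 4.1.1) collects the year of first nodule and the year of diagnosis separately, and SAP 4.2.2 lists the time since each as its own baseline characteristic. A subject may have had nodules for more than 10 years and a diagnosis for fewer, so the two would classify some subjects differently.

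Three things follow if the appendix is programmed as written:

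- Missing Week 16 values of the primary endpoint are imputed without a factor that the ANCOVA then adjusts for.
- The imputation departs from the rule in SAP 4.6, although SAP section 6 declares no change from the protocol's analyses.
- Step 3 needs categories for time since diagnosis and none are defined. The only cut in the documents, at 10 years, belongs to first nodule. The programmer must invent a cut or silently substitute the nodule stratum.

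SAP 4.6.4 carries the primary method over to the other continuous endpoints, so the same error would follow there. The key secondary responder endpoints are unaffected, because SAP 4.6.3 counts missing values as non-response.

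**Working it through.** **Comparison of the passages**

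| Place | Duration variable |
|---|---|
| Protocol 4.1.2.2 and 5.3; SAP 1.2 (randomization) | first nodule, 10 or more vs under 10 years |
| SAP 1.4 Table 1 and 4.6.2 (primary ANCOVA) | first nodule, same cut |
| SAP 4.6.3 (CMH tests) | first nodule, same cut |
| SAP 4.6.5, Table 8 (subgroups) | first nodule, same cut |
| SAP 7.1 step 2, text and code | first diagnosis, called a stratification factor in the text |
| SAP 7.1 step 3, text and code | first diagnosis, called a covariate in the text |

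The mismatch therefore does not rest on one typing slip or on a token broken in the PDF conversion.

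**Scale, from the plan's own figures (SAP 1.5)**

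- Difference 53 − 30 = 23 points, SD 35, two-sided alpha 0.05, 80% power. A two-sample t-test needs 37.34 per arm, rounded up to 38 (power 80.7%).
- 38 / 0.85 = 44.7, rounded up to 45 per arm; 4 × 45 = 180. The stated sample size reproduces, and the correction does not touch it.
- Unadjusted standard error of one comparison: 35 × √(2/45) = 7.4 points.

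**Size of the effect**

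The documents give neither the effect of the nodule stratum on itch nor the number of subjects who change stratum between the two dates. These inputs are assumed: a stratum effect of 5 to 10 points, and 10% to 50% of subjects with nodules for 10 years or more diagnosed under 10 years ago. Missingness is set at 15%, the drop-out in SAP 1.5. The share actually imputed may be lower, because off-treatment data are kept and rescue users get their worst value carried forward.

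*Systematic shift.* Large-sample simulation: 100,000 subjects, two arms, 16 weekly scores, half the subjects in each nodule stratum. There are 54 settings (2 stratum effects × 3 shares moved × 3 correlation structures × 3 drop-out weeks). Absolute change in the Week 16 treatment difference, diagnosis stratum versus nodule stratum in the imputation model:

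| Missingness | Minimum | Median | Maximum |
|---|---|---|---|
| Equal | 0.0002 | 0.0015 | 0.0092 |
| Moderate imbalance (active arm 20% vs 10% by stratum, placebo 15%) | 0.006 | 0.038 | 0.152 |
| Extreme imbalance (30% vs 0%) | 0.024 | 0.119 | 0.471 |

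The worst case is 0.47 / 7.4, about 6% of one standard error. Adding diagnosis to the nodule stratum, instead of replacing it, changes the difference by at most 0.0005 point.

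*Single trials.* With 4 × 45 subjects, equal missingness and 1,500 runs per setting, the mean change is between −0.002 and 0.019 point. The 95th percentile of the absolute change runs from 0.27 to 0.80 point, or 0.27 / 7.63 ≈ 4% to 0.80 / 8.01 ≈ 10% of the simulated standard error.

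*Separate check with random-draw imputation and Rubin's rule.* With 45 per arm, a stratum effect of 0 to 20 points, 60% to 95% agreement between the two strata, and missingness of 25% vs 5% by stratum, the mean estimate moved by at most about 0.03 point. The mean standard error (about 7.7) moved by at most about 0.02.

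*Side point on step 2.* Step 2 has no class statement, so treatment enters there as a numeric code, while step 3 treats it as categorical. With 30% of subjects having one intermittent gap, the effect on the Week 16 difference is at most 0.010 point.

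**The case against.** The strongest reply is that this is a naming error, not a wrong model. Step 2 introduces the variable as an actual stratification factor, echoing SAP 4.6; the trial has only two such factors; and a class statement suits a two-level stratum better than a count of years. The code is also labelled as sample code, and SAP 4.6.2 itself fixes the input subjects, the number of imputations and the combination rule.

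Much of this stands. A mislabelled stratum is a plausible reading, and on it no factor is omitted. Appendix 7.1 is the sole source only for the covariates and steps. But the label of sample code does not cover the prose of steps 2 and 3, which names the same wrong variable, and nothing elsewhere in the SAP tells the programmer which reading to take.

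Three reservations about the numbers are also fair. The large-sample simulation leaves out baseline and sex. The trial-size simulation uses mean prediction instead of 40 random draws. The 0.27 to 0.80 point range is random variation between two imputations, not bias. The numbers show that the effect is small; they are not the reason for the correction. Finally, the appendix uses percent change at Weeks 1 to 16, which fits only the weekly itch score, so its use for scales with fewer visits needs adapting in any case.

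**Conclusion.** The concern holds as a minor correction. The specification of the primary imputation model contradicts the randomization, the analysis model and the SAP's own rule on stratification factors, and it leaves a categorical variable without defined categories. Under the assumed inputs, the systematic effect on the Week 16 treatment difference is below 0.01 point with equal missingness, at most about 0.15 point with moderate imbalance and at most 0.47 point with extreme imbalance, against a standard error of about 7.4 points. Sample size, alpha, power and the responder analyses do not change. The case rests on consistency and reproducibility of a pre-specified primary analysis, not on material bias.

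**What to change.** In the text and code of steps 2 and 3 of Appendix 7.1, replace time since diagnosis with the actual stratum from the EDC data: years since first nodule, 10 or more versus under 10. If time since diagnosis is wanted as well, keep it only as an additional auxiliary variable, named as such.

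As a secondary consistency point, enter treatment in step 2 as three 0/1 arm indicators so that it matches step 3, keeping one imputation model for all arms.

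The cost is one phrase in two text lines and two code blocks, plus the indicators. The year of first nodule is already collected, so neither data collection nor design changes. Make the change before database lock.

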The Phase 2a in PN patients, under the regimen of 720 mg loading dose with up to 15 weekly 360 mg SC doses, demonstrated clinical efficacy and an acceptable safety profile. The  $C_{max}$  and  $C_{trough}$  were 235 and 220  $\mu$ g/mL at week 16, respectively, in the 16-week dosing cohort. Clinical efficacy persisted when drug concentration dropped to approximately 30  $\mu$ g/mL among responders 9 weeks after last dosing. However, it is not certain if  $C_{eff}$  is 30  $\mu$ g/mL or lower as the follow-up period may be insufficient. Additionally, the observed exposure metrics from interim PK samples were largely comparable with predicted concentration-time profiles using the updated PK model (including all subjects from KPL-716-C001). This model was thus used to conduct regimen simulation for Phase 2b. Four repeated doses of 540 mg Q4W could reach a steady status with  $C_{trough} \geq 10, 20, \text{ or } 30 \mu\text{g/mL}$  in 95%, 77%, or 51% of subjects, respectively; therefore, this regimen could be efficacious if  $C_{eff}$  is 30  $\mu$ g/mL or lower. Four repeated doses of 360 mg Q4W SC could reach a steady status with  $C_{trough} \geq 5 \mu\text{g/mL}$  in 88% of subjects and  $C_{trough} \geq 10 \mu\text{g/mL}$  in 68% of subjects. This regimen could provide a reasonable coverage for an estimated  $C_{eff}$  of 5-8  $\mu$ g/mL concluded from the cynomolgus monkey itch model study. Four repeated doses of 120 mg Q4W SC could reach a steady status with  $C_{trough}$  above 5 or 10  $\mu$ g/mL in 1.6% or 0.1% of subjects, respectively. Thus, 120 mg Q4W SC is chosen as a subtherapeutic dose. A 16-week treatment/observation is used to allow for at least 4 repeated doses of each regimen to reach steady status. No loading dose is planned to avoid masking onset of efficacy and efficacy differentiation among the different dose regimens. Per the PK simulation, continuous treatment in OLE with 360 mg, SC, Q2W results in at least 96% or 82% of subjects with  $C_{trough} \geq 10 \text{ or } 20 \mu\text{g/mL}$  and  $C_{max}$  and  $C_{trough}$  (i.e., < 100  $\mu$ g/mL) is below the level achieved in the Phase 2a QW dose but higher than the Q4W doses in the blinded portion of the study. It follows that the proposed Q2W OLE dose provides a more robust drug coverage than the Q4W doses while assumed at least as safe as higher Phase 2a QW exposures, thus complementing the exploration for an efficacious and safe dose overall.

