1.5. Determination of Sample Size

The Phase 2b sample size calculation is based on the primary efficacy endpoint (percentage change from baseline of WI-NRS at Week 16) using a two-sample t-test.

Approximately 180 subjects in total will be equally randomized to the 4 arms of Phase 2b. At Week 16, 53% and 30% reduction in weekly average of WI-NRS are assumed for KPL-716 and placebo arms, respectively. For each comparison, assuming treatment effect of 23% difference in weekly average WI-NRS reduction from baseline at Week 16 and standard deviation of 35%, and two-sided alpha of 0.05, 38 subjects in each arm will provide 80% power to detect the treatment effect. Approximately 45 subjects in each arm will be randomized assuming 15% drop out during the 16 weeks of treatment.

The sample size calculation was performed using nQuery version 8.5.

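### Step 2 of the multiple imputation enters the four arms as one numeric column, which puts a straight line across arms on the filled-in weekly itch scores; the Week 16 contrasts are barely touched

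*SAP*

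**What the plan says.** SAP 4.6.2 sends the reader to SAP 7.1 for the imputation behind the primary analysis. The appendix splits the work in two.

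- **Step 2** fills gaps that lie before a subject's last observed week: "Impute intermediate missing data. 40 datasets with a monotone missing pattern will be obtained". The call is "mcmc impute=monotone". Its variable list begins "var sex years since_first_diagnosis baseline treatment_group" and goes on to Weeks 1-16. It has no CLASS line. The text agrees with the code and names treatment as one item: "Variables in MCMC modeling includes actual stratification factors: sex, years since first PN diagnosis, treatment, baseline score, and percent change scores of weeks 1-16".
- **Step 3** does the rest: "the remaining missing data will be imputed using the regression method for the monotone pattern". Here the variable is categorical: "class sex years since_first_diagnosis treatment_group".

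The trial has four arms ("Approximately 180 subjects in total will be equally randomized to the 4 arms of Phase 2b"). SAP 4.6.2 fits treatment as a fixed-effect factor and tests each dose separately against placebo. SAP 4.6.4 analyses the other continuous change and percent-change endpoints, including weekly WI-NRS over time, in the same way as the primary endpoint.

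**The concern.** In a two-arm trial a single 0/1 treatment column in an MCMC model is harmless. With four arms, one numeric column says that equal steps in the code mean equal steps in the outcome. The SAP gives no code, so the imputed values depend on a choice nobody has recorded.

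Neither the planning assumption nor the aim supports that shape. SAP 1.5 assumes a 53% reduction on KPL-716 and 30% on placebo, which is a step and not a line. Protocol 4.5 sets out to find the minimally efficacious dose, so the shape across arms is the question under study. An imputation model narrower than the analysis model pulls imputed values toward a pattern that the analysis is meant to test freely.

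The endpoints directly exposed are weekly change and percent change in WI-NRS in Weeks 1-15, because Step 2 fills those gaps.

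**Working it through.** **Inputs.** From SAP 1.5: mean changes of -53 (KPL-716) and -30 (placebo), SD 35, two-sided alpha 0.05, 80% power, 15% dropout. From SAP 1.2: arms A-D = 540, 360, 120 mg and placebo, allocated 1:1:1:1. Not in the documents, so assumed: arm code, between-week correlation, intermittent missingness and time course.

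**The plan's own figure.** 2 × (35/23)² × (1.960 + 0.842)² = 36.4, so 37 by normal approximation. The exact t-test gives 79.6% power at 37 and 80.7% at 38, hence 38. Then 38/0.85 = 44.7, hence 45. Both SAP figures reproduce, and nothing below changes them.

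**The line itself.** For codes x = 1 to 4, slope = Σ(x - 2.5)·mean / 5.

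| Profile A, B, C, D | Code | Fitted A, B, C, D | A, B, C minus placebo |
|---|---|---|---|
| -53, -53, -53, -30 (SAP 1.5) | A-D = 1-4 | -57.6, -50.7, -43.8, -36.9 | -20.7, -13.8, -6.9 (true: -23 each) |
| same | placebo = 1, A-C = 2-4 | -43.8, -50.7, -57.6, -36.9 | -6.9, -13.8, -20.7 |
| -53, -53, -30, -30 (assumption) | A-D = 1-4 | -55.3, -46.1, -36.9, -27.7 | -27.6, -18.4, -9.2 (true: -23, -23, 0) |

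First row: slope = (79.5 + 26.5 - 26.5 - 45)/5 = 6.9 about a mean of -47.25. The misses (fitted minus true) are -4.6, +2.3, +9.2 and -6.9. In the third row they are -2.3, +6.9, -6.9 and +2.3. Recoding reverses the fitted order of the doses.

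**What survives conditioning.** These misses are marginal. Step 2 also conditions on the subject's other weeks. If m is the miss in each week and b the weight on each other week, the shift in an imputed value is m(w) - Σ b·m(j). With exchangeable correlation ρ, b = ρ/(1 + 14ρ).

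- Arm effect constant over weeks, ρ = 0.7: b = 0.0648, and 1 - 15b = 0.028 remains. The largest miss shrinks from 9.2 to about 0.26. Under AR(1) 0.7 about 6% remains at interior weeks, but 30% (2.8 points) at Week 1.
- Effect growing linearly to Week 16, ρ = 0.7, so m(j) = 0.575·j. Week 1: 0.575 - 0.0648 × 0.575 × 135 = -4.5. Week 15: 8.63 - 0.0648 × 0.575 × 121 = +4.1. Averaged over Weeks 1-15: 4.6 - 0.0648 × 73.6 = -0.2. The median absolute shift is 2.3; under AR(1) 0.7 it is 0.3.

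Early and late weeks err in opposite directions, so an average over weeks looks smaller than a single week can be. With 20% of Week 1 values filled this way, the Week 1 arm mean would move by 0.20 × 4.5 = 0.9 point; with 5%, by 0.2.

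**Simulation of Steps 2 and 3.** Numeric column against three indicators, with 15% dropout, 5-20% intermittent missing weeks completely at random, an exponential time course, and sex, duration and baseline omitted. Largest absolute shift over the profiles, codes and missingness rates run:

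| Between-week correlation | Step 2 values, per arm, averaged over weeks | Week 16 difference from placebo |
|---|---|---|
| 0.3 | about 1.0 | 0.07 |
| 0.6 | about 0.2 | 0.08 |
| above 0.9 | about 0.1 | 0.01 |

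**Why Week 16 is spared.** Week 16 is last in the variable order, so a missing Week 16 value is never intermediate. No Week 16 value was filled in Step 2 in any scenario. Step 2 reaches the primary endpoint only through filled earlier weeks, which serve as predictors in the Step 3 regression.

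**The case against.** The appendix calls this sample code. It gives no arm code, the call as printed would need editing before it ran, and a character treatment variable could not enter MCMC at all. A programmer must recode, and three indicators would be consistent with prose that simply names treatment. That is fair: the numeric column is an inference about following the text as printed. But SAP 4.6.2 relies on this appendix, no other text specifies the model, and Step 3 shows that the same column is meant.

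The arm letters run in dose order, so the code need not be arbitrary. True, but order is not linearity. Coding by mg (540, 360, 120, 0) still misses the third profile in the table by -3.1, +6.1, -4.6 and +1.5.

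The scope is narrow, and this stands. Responder endpoints use non-responder imputation (SAP 4.6.3, 4.6.4). Both sensitivity analyses of the primary endpoint drop multiple imputation. Subjects with rescue or prohibited medication are excluded from its input. SAP 3.3 sets no minimum number of diary days for a post-baseline weekly mean, so wholly missing weeks between observed ones may be few.

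A reader might infer two stronger things. The first is that the primary dose comparisons are materially biased; the order of imputation and the simulation do not support it. The second is that the sponsor expects 120 mg to act like placebo. Protocol 4.5 says only "Thus, 120 mg Q4W SC is chosen as a subtherapeutic dose", on the basis of simulated trough concentrations, and predicts no itch response. The -53, -53, -30, -30 profile is therefore an illustration; the point does not need it.

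**Conclusion.** A minor specification error that should be corrected. As printed, Step 2 treats the four arms as points on a line, while Step 3 and the ANCOVA treat them as categories.

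The direct effect is confined to Weeks 1-15 of the weekly change and percent-change WI-NRS endpoints: about 1 point per arm or less in the filled values, averaged over weeks, at correlation 0.3, and about 0.2 or less at 0.6 and above. Single edge weeks can be off by 4 to 5 points per imputed value if the effect grows over time and correlation does not decay. The effect on an arm mean is that shift times the share of values imputed. Primary Week 16 contrasts move by less than about 0.1 point against 23, and the sample size is unaffected.

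These sizes rest on assumed correlation, missingness and time course. The mismatch between the two steps does not.

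**What to change.** In Step 2, replace `treatment_group` with three 0/1 arm indicators in the VAR list, and say so in the Step 2 text. Keep `treatment_group` as CLASS in Step 3.

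Two apparent alternatives are not advised. Adding a CLASS line to the MCMC call is not sufficient, because that model treats its variables as continuous. Running Step 2 separately by arm would estimate 19 means and 19 × 20/2 = 190 variances and covariances (sex, duration, baseline, 16 weeks) from about 45 subjects per arm or fewer.

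The cost is one line of code and one phrase of text, with no change to design, data collection or sample size.
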